#### C. Molecular characteristics.

The following variables are known to influence efficacy of tamoxifen in the treatment of BC patients and will be analyzed at a later date.

*Endoxifen levels* – continuous, time-varying. These data will be available at t1 and t2.

*CYP variants* - dichotomous (yes/no), constant over the study period.

In addition to testing their significance as effect modifiers, we will also examine their relationship with the outcome variables (MBD, cytomorphology, proliferative index, etc) to validate known relationships. Proc Mixed for normal data and Proc GLMMIX for non-normal data in SAS 9.1 (Cary, North Carolina) will be used for analysis.

***Exploratory Aim 2: To examine the relationship between a low-dose tamoxifen regimen and clinical measures of efficacy and toxicity.***

For measures of clinical efficacy, we will document the occurrence of new breast cancer and DCIS diagnoses.

The assessment of clinical toxicity will include the following outcomes/measures:

- 1) incidence of uterine and other cancers during the study;
- 2) gynecological symptoms: any and the frequency of hot flashes, night sweats, vaginal discharge, vaginal bleeding or spotting, missed menstrual periods for pre-menopausal women, genital itching/irritation, and pain with intercourse, to be obtained from symptom log administered 10 times (baseline, days 28, 90, 180, 270, 365, 455, 540, 630, 730) ;
- 3) incident thromboembolic events (DVT, PE, TIA or stroke, and retinal vein thromboses);

4) incidence of cataract;

5) liver function abnormalities: total bilirubin, SGOT/AST, SGPT/ALT, measured at baseline, year 1, and year 2.

The *incidence* of new breast cancer, DCIS, non-breast malignancies, thromboembolic events, and cataract are expected to be low ( $\leq 5$  events per arm) during the study period given the sample size, based on statistics quoted in Investigational Brochure. Thus, we will initially compare the frequency of events by treatment group in a 2x2 table using the Fisher exact test, stratified on CYP2D6 status. We will also use poisson regression in cohort analysis to examine treatment differences in these outcomes adjusted for covariates, including CYP2D6.

The presence/absence of gynecological symptoms (for each symptom mentioned above) will be compared between treatment groups using 2x2 tables using the Fisher exact test, stratified on CYP2D6 status. Logistic regression will be used to compare the frequency between treatments adjusted for covariates, including CYP2D6. Longitudinal analysis also will be conducted to compare the trends of the presence/absence of each of the reported gynecological symptoms over the 2 year period using the generalized linear mixed-effects model for binary outcomes.

For each liver function measure, a woman will be considered to have elevated liver function if the measurements at years 1 and/or 2 are above the upper limit of the institutional reference range and higher than her baseline pre-treatment level. These data will be coded such that those who are greater than 2-times the upper limit of the reference range will be considered to be clinically significant (grade 1 if asymptomatic and requiring no intervention; grade 2 if minimal/local/non-invasive intervention required). The frequency of women with elevated liver function measures will be compared between treatment groups using an exact test on 2x2 tables, stratified on CYP2D6. Logistic regression analysis will also be used to compare the frequency of elevated liver function between treatments, adjusted for covariates. Linear mixed-effects model for normally distributed data will also be used to compare the trends in liver function levels between the treatment groups. Procs MIXED and GLIMMIX will be used for longitudinal analysis of normally and non-normally distributed data, respectively. Poisson regression analysis will be conducted using Proc GENMOD, all in SAS 9.1 (Cary, North Carolina).

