### 3.5 **Supplier**

Tamoxifen is commercially available in 10 mg and 20 mg tablets. For this trial, generic 5mg capsules and matching placebo capsules will be manufactured by Sharp Clinical Services.

Tamoxifen and matching placebo will be manufactured as a capsule for oral administration. Each 5 mg tamoxifen capsule contains 7.6 mg of tamoxifen citrate, which is equivalent to 5 mg of tamoxifen, as well as anhydrous lactose, colloidal silicon dioxide, crospovidone, magnesium stearate, microcrystalline cellulose and sodium lauryl sulfate, as inert excipients. Matching placebo capsules will contain anhydrous lactose.

For this study, blistered cards will contain a month's supply of tamoxifen 5mg or matching placebo capsules.

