  - systemic hormone replacement therapy (includes oral or transdermal formulations). Vagifem and Estring, two formulations of locally applied vaginal estrogen associated with minimal systemic absorption, may be allowed. Other estrogen-containing vaginal creams, while not an exclusion, should be avoided whenever possible. Patients with a history of hormone modifying herbal supplements (see section 11.14) are eligible, but patients will be asked to avoid their use after on study.
  - hormonal forms of contraception (includes oral, transdermal, implanted, and injectable formulations),
  - selective estrogen receptor modifiers (such as tamoxifen and raloxifene),
  - aromatase inhibitors,
  - GnRH analogs,
  - prolactin inhibitors, or
  - androgens or antiandrogens.
- Concurrent use of warfarin and strong inhibitors of CYP2D6 (see Section 11.15 for a list) will not be allowed.
- A personal history or a strong family history of venous thromboembolism, (VTE), including deep venous thrombosis (DVT) or pulmonary embolus (PE). A one-time personal history of catheter-associated DVT may be allowed, as long as there were no subsequent VTE events and a strong family history is not present. Examples of a strong family history include (but are not limited to): one first degree relative with more than one VTE event in the same individual, and two family members in the same lineage with unexplained VTE or two VTE events in the same individual. If a family history is present, but it is not clear whether or not it is clinically significant, consideration of genetic testing to rule out a hereditary clotting syndrome (e.g. FVL, prothrombin G2010A mutations) may be considered. Because of a drug-drug interaction with tamoxifen, concurrent with warfarin use for any reason is not allowed.

For this reason, patients with atrial fibrillation may not participate. However, patients with coronary artery disease or congestive heart failure without atrial fibrillation may be allowed to participate. Patients with a personal history of a cerebrovascular accident (CVA), transient ischemic attack (TIA), or retinal vein thrombosis will not be allowed to participate.

- Current intrauterine pregnancy or plans to become pregnant within two years. In addition, currently nursing mothers will be excluded.
- Renal or hepatic insufficiency, defined as having a serum creatinine, total bilirubin, SGOT, or SGPT greater than 2x the institutional norm.
- Unable to provide consent.

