**Subjective safety and tolerability measures:**

**Treatment adherence.** Compliance will be measured by pill counts performed every 3 months. The number of pills taken out of the total prescribed in a 3-month period will be modeled as a random effects binomial regression model [105]. The binomial rates from 8 time points (month 3 to 24) will be modeled as unstructured mean model with 7 indicator variables as well as polynomial models over time. The random-intercept and the random intercept and slope models will be considered. The significance of the time indicators or parameters by treatment interaction will be evaluated for treatment difference in compliance.

Voluntary withdrawals will be examined at the end of the study by comparing the percent of withdrawals between the treatment groups using a chi-square test or Fisher's exact test.

**Patient reported symptoms.** The outcomes will be scored as a 5-point Likert-type scale (0 to 4) in response to questions on how much the patients are bothered by certain symptoms. The questionnaire will be administered every six months, for a total of five time points. The responses will be treated as normally distributed, as ordinal or dichotomized variable, and we will apply the linear mixed effects model or GLMM methods to compare changes between treatment groups. Because of additional time points available, in addition to the unstructured mean model, we will also fit piecewise models with join point at 6 months, considering linear and curvilinear trajectories between 6m and 24m time points.

***Exploratory Aim 1: To examine the modifying effects of demographic, clinical, and molecular characteristics on both efficacy and safety markers.***

As the primary aim of this trial is to examine the main effects of low dose tamoxifen treatment on MBD, we will examine the modifying effects of demographic, clinical, and molecular characteristics as exploratory analysis. Even if time by treatment interaction (main treatment effect) is not significant, examining the modifying effects of covariates may reveal subgroups that respond differently to low dose tamoxifen. A three-way interaction of time by treatment by modifying variable will be included in the longitudinal model containing a two-way time by treatment group interaction. Modifying effects will be considered statistically significant if the three-way interaction is significant. The covariates of interest are described below.

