#### A. Patient demographics.

The following variables are known to affect breast cancer risk and MBD.

*Attained age* – continuous, time-varying variable.

*Menopausal status* – status at study enrollment (premenopausal or postmenopausal, as defined in Section 5.0) will be considered as constant over the study period. We will also consider trichotomized status (pre-menopausal, typical post-menopausal, and early post-menopausal), constant over the study period. Menopause will be defined as “early” if onset was before age 50.

*Prior hormone use* – categorical variable (estrogen plus progestin menopausal hormone therapy, estrogen-only menopausal hormone therapy, hormonal contraception and/or fertility drugs, no prior hormonal therapy). We will also consider duration of use, as a continuous and dichotomous variable (5+ years, <5 years); and most recent use (within 1 year, >1 year).

*Body mass index (BMI)* – continuous, time-varying variable. It will also be grouped into ordinal categories: underweight (<19), normal weight (19-24), overweight (25-29), obese (30-39), morbidly obese (40+).

*Personal history of benign breast disease* – dichotomous (yes/no), constant over the study period. We will also examine whether the number of prior breast biopsies, and the presence of atypia or LCIS on a prior biopsy further modifies the intervention effect.

*Family history of cancer* – dichotomous (yes/no), constant over the study period. We will also examine the frequency of the following classifications: 0 = no family members with breast cancer; 1 = one or more first or secondary degree relative(s) with BC all diagnosed at 50+ years of age; 2= one first or second degree relative with BC diagnosed

before age 50 (or two, but on different sides of the family); 3 = two or more first and/or second degree relatives with BC diagnosed before age 50 and/or ovarian cancer on the same side of the family; 4 = carrier of a germline mutation in a highly penetrant BC susceptibility gene (BRCA1, BRCA2, PTEN, p53), or a known mutation in one of these genes in the patient's family and patient has not had genetic testing. If this results in sparse cells, we will consider collapsing them: A = no family history, B = some family history (group 2 above), and C = strong family history (groups 3 and 4 above). We will also examine if the number of first & second degree relatives (constant over the study period) is a significant effect modifier.

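### Endoxifen cannot be tested as a modifier of the treatment effect, because it is zero in the placebo arm and the planned three-way term is therefore only time by endoxifen.

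*Combined protocol and SAP*

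**What the plan says.** Section 12.4, Exploratory Aim 1, sets one model for all modifiers: "A three-way interaction of time by treatment by modifying variable will be included in the longitudinal model", added to a model that already holds time by treatment. The decision rule is "Modifying effects will be considered statistically significant if the three-way interaction is significant". The status is stated plainly: "we will examine the modifying effects of demographic, clinical, and molecular characteristics as exploratory analysis".

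The covariates follow in three lists. List C (molecular characteristics) has two entries:

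- Endoxifen, continuous and time-varying: "These data will be available at t1 and t2".
- CYP variants, yes/no and constant over the study.

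The text after list C confirms that both are meant for the modifier test ("In addition to testing their significance as effect modifiers") and adds that their relation to the outcomes will also be examined. It defers the molecular analyses to a later date.

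In list A (patient demographics), BMI is "continuous, time-varying variable. It will also be grouped into ordinal categories". Menopausal status, by contrast, is held at its enrolment value.

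On the placebo, Section 3.5 says "Matching placebo capsules will contain anhydrous lactose". Section 5.2 excludes women who used a selective estrogen receptor modifier in the 6 months before registration or the baseline mammogram, and Section 11.16 lists other drugs of that class to avoid on trial.

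**The concern.** An effect modifier is a characteristic, defined in both arms, across whose levels the difference between arms varies. Endoxifen is a product of the study drug. It has no counterpart on placebo, so there is no treatment difference at a given endoxifen level to compare with the difference at another level.

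The plan nevertheless sends endoxifen through the same test and significance rule as menopausal status or radiation dose. Nothing in Section 12.4 restricts it to the tamoxifen arm or says how placebo values are coded. Objective 1.3 names molecular characteristics among the modifiers, and Section 2.6 hypothesises a subgroup with the most benefit and least risk. A significant endoxifen term could therefore be read as evidence for that subgroup, although drug level within one arm also reflects adherence, metabolism and interacting drugs, none of which is randomised.

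**Working it through.** **Inputs.** Three time points t0, t1 and t2; treatment A = 0 (placebo) or 1 (tamoxifen); endoxifen E. The two mean models are those of Section 12.4: unstructured (two time indicators) and linear in time. The plan gives no figure for this test to reproduce.

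**Step 1: E on placebo.** The placebo contains no tamoxifen. For carry-over, Section 3.4 gives a half-life of 5 to 7 days for tamoxifen and about 14 days for N-desmethyl-tamoxifen, which Section 11.11 equates with endoxifen. Six months is about 180 days, and 180/14 is about 13 half-lives before registration; t1 is a year later still. So E = 0 wherever A = 0, assuming that no placebo woman obtains tamoxifen outside the trial.

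**Step 2: algebra.** If A = 0 then A × E = 0 = E. If A = 1 then A × E = E. Hence A × E = E in every row, and time × A × E = time × E. This does not depend on how E is coded at t0, where no value is planned.

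**Step 3: rank of the fixed-effects design.** 100 women per arm; E set to zero on placebo and at t0, positive and variable on tamoxifen afterwards; all lower-order terms included, as in the menopause example of Section 12.5.

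| Model | Columns | Rank | Rank without the three-way term |
|---|---|---|---|
| Endoxifen, unstructured mean | 12 | 8 | 8 |
| Endoxifen, linear in time | 8 | 6 | 6 |
| Menopausal status, linear in time (control) | 8 | 8 | – |

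Removing the endoxifen three-way term leaves the rank unchanged, so the test has nothing of its own to estimate. Menopausal status, defined at baseline in both arms, gives a full-rank model.

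**Step 4: other ways to fit it.**

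- *Placebo values set to missing.* All placebo rows drop out, treatment is constant, and no treatment interaction exists.
- *Lower-order endoxifen terms omitted.* The model is full rank (8 of 8 columns unstructured, 5 of 5 linear). But E varies only on tamoxifen, and time by treatment already absorbs the arm means, so the coefficient is the slope of density on drug level among treated women. The plan's rule would call it a modifying effect.

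No coding yields a test of effect modification.

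**Step 5: BMI.** The BMI three-way term can be estimated, because both arms have BMI. The question is interpretation: values at t1 and t2 come after randomisation and could be altered by treatment. To see whether this alone creates a false interaction, the linear model was simulated under assumed inputs: 100 per arm, correlation 0.8, root density falling 0.05 or 0.10 per BMI unit, and treatment shifting BMI by 0, 0.5, 1 or 2 units at t2. The mean three-way estimate was at most 0.001 in absolute value, with rejection rates of 3.4% to 6.6%. A uniform shift in a linear model does not produce a false interaction.

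**The case against.** **The aliasing depends on terms that Exploratory Aim 1 does not list.** The aim's text adds the three-way term to a model with time by treatment and does not mention an endoxifen main effect or time by endoxifen; those appear by analogy only in the menopause example of Section 12.5. This stands. A reader might infer that the test can never be computed or has no degrees of freedom, but that holds only for the hierarchical model. Without the lower-order terms a number comes out; it answers a different question.

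**The remedy is partly present.** The plan will also relate endoxifen to the outcomes, lists CYP variants as a modifier, and in its as-treated analysis replaces the treatment indicator by adherence, coded 0 for placebo. This also stands, and it shows that the authors know how to handle a quantity of this kind. But the outcome sentence is expressly additional to the modifier test, is not confined to the tamoxifen arm and is not labelled non-randomised.

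**BMI.** A reader might infer that time-varying BMI will generate spurious subgroups. The documents do not support this: they give no effect of tamoxifen on BMI, and the simulation found no false interaction from a uniform shift. A non-linear or heterogeneous BMI effect would be needed, and nothing in the documents establishes one.

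**Attained age and latency.** These are also time-varying, and a reader might extend the point to them. They advance with the calendar and treatment cannot change them, so they do not share the fault.

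**Consequence.** The analyses are exploratory, deferred, and openly low in power (40%, 24% and 12% in the menopause example). Under hierarchical coding the redundancy would show when the model is fitted. This limits the importance of the point but does not make the stated test valid.

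**Conclusion.** The point holds for endoxifen: the stated rule gives no valid result for effect modification. In a hierarchical model the term is exactly redundant; in a reduced model it is a within-tamoxifen exposure-response slope under the wrong name. The conclusion rests on endoxifen being zero on placebo, which follows from the capsule contents and the drug exclusions unless a placebo woman takes tamoxifen outside the trial.

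For BMI the conclusion is weaker. Subgroups defined by on-treatment BMI may not be randomised comparisons, so baseline BMI is the better modifier. The size of any problem is unknown, and no false interaction has been demonstrated.

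The importance is low. The primary density test and the 230-woman sample size do not depend on these analyses.

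**What to change.** In Section 12.4, Exploratory Aim 1:

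1. Remove endoxifen from the variables tested by the three-way interaction.
2. State that endoxifen will be analysed in the tamoxifen arm only, through its association with density over time (time by endoxifen), and label this a non-randomised exposure-response analysis.
3. Keep CYP genotype as the molecular modifier. It is constant and defined in both arms, so its three-way term can be estimated provided that each genotype group occurs in both arms.
4. Secondary: use BMI at t0 as the modifier, as is already done for menopausal status. Any model with on-treatment BMI can be kept as a labelled descriptive supplement.

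The cost is a few sentences of plan wording. No further participants, visits or assays are needed. The change should be made before the deferred molecular data are analysed.

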## 12.5 Power and sample size:

***Aim 1:*** *To determine the impact of low-dose tamoxifen on surrogate endpoint biomarkers of BC risk.*

**Mammographic breast density (MBD):** The primary efficacy endpoint of the trial is MBD. The efficacy of low dose tamoxifen will be examined by comparing the slopes in the longitudinal linear regression of the MBD on time since treatment initiation between the low dose tamoxifen group and placebo control group. For sample size calculation, we let Y, the response, as the mean of the square root of MBD (RTMBD) from both breasts. Because of randomization, we expect no difference between the expected values of Y at t0 between treatments but expect the linear slopes of the two groups to diverge over time, if the intervention is efficacious. Power/sample size calculation was conducted by assuming a linear change in RTMBD over time and various magnitudes of RTMBD difference expected at t2 between the treatment and control groups.

Longitudinal power calculation requires specification of the expected linear trend (thus the expected values of Y at t0, t1, t2) for the controls, the variance/covariance of the repeated measurements, the expected difference in Y at t2 between the treatment groups, and the correlations among repeated measurements. These estimates were obtained from 41 control women in the Puget Sound NSABP P-1 participating sites, [106] 16 pre-menopausal women (median age=50, range=38-50) and 25 post-menopausal women, (median age=57, range=36-74), with data on MBD expressed as a percent breast density at pre-, 1-yr, and 2-yr post-treatment. Although this entire control sample (median age=50, range=36-74) is older than the available CPIR HL cohort (median age=35, range 25-50), based on changes in MBD observed with hormonal fluctuations during the menstrual cycle [66] and after discontinuation of exogenous hormone in postmenopausal women [70], it can be reasonably assumed that estrogen withdrawal associated with menopause has a greater impact on variation in MBD than age alone. Thus, we assumed that the estimates obtained from these women can be applied to the anticipated CAYAC patient control sample.

The expected RTMBD at the three time points in the pre-menopausal and post-menopausal women in the Puget Sound sample were estimated longitudinally using SAS Proc Mixed with a compound symmetry covariance structure. Square root transformation was used to normalize the distribution. A significant decline in MBD with time was detected. Since the covariance matrices of the pre- and post-menopausal women looked very similar, for simplicity, they were assumed to be equal. To determine the variance/covariances of the MBDs and the expected values at t0, t1, t2 in the anticipated CAYAC sample, 1000 random trials of size n were generated from multivariate normal distributions with parameters estimated from the Puget Sound sample to simulate the CAYAC sample expected to contain 67% pre-menopausal and 33% post-menopausal women. Sixty-seven percent of n were drawn randomly from a multivariate normal distribution with expected MBD of (24.7, 23.57, 22.27) at (t0, t1, t2) as predicted for Puget sound pre-menopausal women, and 33% of n were drawn randomly from a multivariate normal distribution with expected Y of (15.49, 11.99, 13.03) as predicted for post-menopausal women. For each of the 1000 simulated samples, a longitudinal linear model was fitted assuming a compound symmetry structure for the covariance. The average of the 1000 estimates of the linear parameter was used to estimate the expected RTMBD at t0, t1, t2 for the CAYAC control sample.

The expected RTMBDs for CAYAC controls obtained from simulations were used to specify the effect size, defined as the difference between expected values at t2 for the two groups divided by the common sd, in the longitudinal power calculations were conducted using the program RMASS2. [107]. We assumed a Type I error of .05, power of .80, 2-sided test, no attrition over time, linear trend, compound symmetry covariance structure, and a correlation of 0.8 between measurements (estimated from the Puget Sound sample).

The size of the difference in MBD that can be detected between the low dose tamoxifen and placebo groups at year 2 (t2) are shown in the table below. Column 4 indicates the expected MBD before randomization (at t0). The expected MBDs at t2 for the control and treatment groups are shown in columns 5 and 6, respectively. Column 7 and Column 8 are the % reduction in MBD at t2 relative to t0 in the placebo control group and low dose tamoxifen treatment group, respectively. The last column shows the % reduction in PD in the treatment group at t2 relative to controls.

Placebo (PBO)	Low Dose Tamoxifen (LDTAM)	Power	Exp(MBD) at t0	Exp(MBD) at t2		% reduction in MBD at t2 relative to t0		% reduction in MBD at t2 for LDTAM group relative to PBO
			Both treatment groups	PBO	LDTAM	PBO	LDTAM	
50	50	.8	21.2	18.75	13.42	11.6%	36.5%	28.4%
		.9	"	"	12.68	"	40.0%	32.4%
75	75	.8	21.1	18.67	14.27	"	32.5%	23.5%
		.9	"	"	13.70	"	35.2%	26.6%
100	100	.8	21.2	18.72	14.89	"	29.6%	20.5%
		.9	"	"	14.32	"	32.3%	23.5%
150	150	.8	21.1	18.64	15.47	"	26.8%	17.0%
		.9	"	"	15.00	"	29.1%	19.5%
200	200	.8	21.1	18.67	15.91	"	24.8%	14.8%
		.9	"	"	15.50	"	26.7%	17.0%

If we anticipate the MBD in the low dose tamoxifen group to change from 21.1 at t0 to 14.89 at t2 compared to 18.72 at t2 in controls (in other words, a reduction of ~30% with low dose tamoxifen versus 11.6% with placebo over a 2 year time, or about 20% reduction in MBD with low dose tamoxifen relative to placebo, or an effect size of 0.25 at t2), a sample size of 100 per arm will be able to detect this magnitude of change with 80% power. With 10% attrition at each annual follow-up visit, 115 women per arm (or a total of 230) would be required. Thus, the goal accrual for this trial will be 115 women per arm, for a total of 230 women at t0.

Tissue and blood biomarkers: Masood score (cytomorphology) and Ki67 expression (proliferative index) evaluated from breast tissue samples will be obtained at t0 and t2. Insulin growth factors (IGF1 and IGFBP-3) will be measured at 3 time points. With a baseline sample size of 115 women per arm (assuming 10% yearly attrition), assuming Type I error=0.05, 2-sided test, and a within-person correlation of 0.5 between pairs of normally distributed measurements, there is 80% power to detect an effect size of 0.34 (absolute difference between treatment and control means divided by the common standard deviation) at year 2. A similar effect size is detectable for Ki67 for which the problem was formulated as that of detecting the difference at t2 in percent of women with positive expression (at least one cell expressing Ki67) between the treatment groups. Kahn et al [86] reported a median Ki67 expression level of 1.4% in RPFNA samples collected from 147 women at high risk for breast cancer. Thus, we hypothesized that 50% (conservative estimate) to 85%.of our cohort will have Ki67 expression in their healthy breast tissue samples collected via RPFNA at their baseline visit.

Detectable values for the various outcomes are shown in the table below. Column 2 shows the assumed common mean ( $\pm$  SD) at t0 for both treatment groups (obtained from the literature, adjusted for the age structure of our cohort, if possible). Column 3 shows the minimum detectable level at t2 for the tamoxifen group in the hypothesized

direction. The mean levels at t2 in the placebo group are assumed to remain the same as those at t0. Column 4 shows the detectable % change at t2 relative to t0 in the tamoxifen group.

Outcome	Assumed levels at t0 for Placebo and Low dose Tamoxifen groups	Detectable levels at t2 (80% power) for Low dose Tamoxifen group	
	Mean ± SD	Mean	% change (from t0)
Masood score 	14 ± 1.8	13.4	4% ↓
Women positive for Ki67 expression  (%)	50%	32%	36% ↓
	65%	47%	28% ↓
	85%	70%	18% ↓
IGF1  (ng/ml)	260 ± 82.5	230	12% ↓
IGFBP-3  (ng/ml)	3346 ± 1226	3787	13% ↑

Thus, we expect to be able to detect a 5-36% difference in the BC risk biomarkers proposed as secondary endpoints.

**Aim 2:** *To establish safety and tolerability of low-dose tamoxifen.*

**Adverse events:** We assume the rate of grade 2-4 toxicities in the placebo group to be low, at 0.5%. At the end of the study, with 94 women in each arm (accounting for 10% attrition per year), the study will have at least 80% power to detect an adverse event rate of 9.1% in the low dose tamoxifen group based on Fisher’s exact test and Type I error=0.05.

**Adherence to therapy:** We will examine the difference in adherence rates of the treatment groups by comparing the percent of pills taken across 8 time points. With 115 women at baseline per arm, assuming a constant adherence rate of 90% in the placebo group and a between-measurement correlation of 0.6 and 2-sided alternative, there will be 80% power to detect an adherence rate of about 77% in the low dose tamoxifen group.

**Voluntary withdrawals:** If the proportion of patients in the placebo arm who withdraws voluntarily by the end of the study is 10%, then with 115 women in each arm at baseline, assuming type I error=0.05, the study will have 80% power to detect a significant difference in the voluntary withdrawal rate in the low dose tamoxifen group if the withdrawal rate in the intervention group is about 28%.

**Safety biomarkers:** We focus here on total cholesterol (TC), anti-thrombin-III (AT-III), bone-specific alkaline phosphatase (BSAP), and urine N-telopeptide crosslinks (NTX). With the proposed sample sizes, the detectable effect size (described earlier) is 0.34. A relatively small % change in mean levels is detectable for TC and AT-III but larger % changes are needed to detect a significant treatment difference at t2 for BSAP and NTX.

Outcome	Assumed levels at t0 for Placebo and Low dose Tamoxifen groups	Detectable levels at t2 (80% power) for Low dose Tamoxifen group	
	Mean ± SD	Mean	Relative % change (from t0)

TC* (mg/dL)	199 ± 45	214.3	8% ↑
AT-III** (%)	100 ± 13.3	95.5	5% ↓
BSAP  (µg/L)	7.7 ± 4.5	6.2	20% ↓
NTX  (nM BCE/mM)	24.4 ± 16.1	18.9	23% ↓

\* Mean obtained from [111], sd obtained from [112]

\*\* per ARUP reference laboratory

Thus, we expect to be able to detect a 5-23% difference in the objective safety biomarkers proposed as secondary endpoints.

